8.3.3 Database Quality Assurance

In accordance with the vendor's procedures, the clinical database will be reviewed and checked for omissions, apparent errors, and values requiring further clarification using computerized and manual procedures. The procedure for handling missing data will be addressed in the SAP. Data queries requiring clarification will be documented and returned to the study site for resolution. Only authorized personnel will make corrections to the clinical database, and all corrections will be documented in an audit trail.

8.3.4 Bioanalytical Sample Handling

Topiramate (TPM) concentrations in plasma samples will be determined using a validated chromatographic method. Details on the analytical methodology, the method of validation, and the analytical within-study quality control procedures will be included in the clinical study report for this study.

8.4 Retention of Records

The Investigator has the responsibility to retain all study "essential documents", as described in ICH E6 for at least 2 years after approval of a marketing application or after formal discontinuation of the clinical program. Essential documents include but are not limited to the protocol, eCRFs, source documents, laboratory test results, SM inventory records, Investigator's Brochure, regulatory agency registration documents (e.g., FDA form 1572, ICFs, and IRB correspondence). The Investigator must obtain written permission from Supernus prior to the destruction of any study document.

8.5 Auditing Procedures

In addition to the routine monitoring procedures, the Sponsor's Corporate Quality Assurance department or qualified designee may conduct audits of clinical research activities in accordance with the Sponsor's written SOPs to evaluate compliance with the principles of ICH GCP and all applicable local regulations. A government regulatory authority may also wish to conduct an inspection (during the study or after its completion). If an inspection is requested by a regulatory authority, the Investigator must inform the Sponsor immediately that this request has been made.

These records must be made available at reasonable times for inspection and duplication, if required, by a properly authorized representative of the US FDA in accordance with the US 21 CFR 312.68 or other national or foreign regulatory authorities in accordance with regulatory requirements.

8.6 Publication of Results

Any presentation or publication of data collected as a direct or indirect result of this trial will be considered as a joint publication by the Investigator(s) and the appropriate personnel at the Sponsor's site. Authorship will be determined by mutual agreement. All manuscripts, abstracts or other modes of presentation arising from the results of the study must be reviewed and approved in writing by the Sponsor, prior to submission for publication or presentation. No publication or presentation with respect to the study shall be made until Sponsor comments on the proposed publication or presentation have been addressed to the Sponsor's satisfaction.

The detailed obligations regarding the publication of any data, material results, or other information, generated or created in relation to the study shall be outlined in the agreement between each Investigator and the Sponsor or designee.

8.7 Financing and Insurance

Financing and Insurance information will be set forth in a separate document between the Investigator and Sponsor (provided by the Sponsor or designee).

8.9 Discontinuation of Study

The Sponsor reserves the right to discontinue the study for medical or administrative reasons at any time. The Investigator will be reimbursed for reasonable expenses covering subjects, use of live-in facilities, laboratory tests, and other professional fees. The Investigator will refund the excess of payments made in advance.

The Investigator reserves the right to discontinue the study as per his/her judgment. The Investigator will notify the IRB in case of study discontinuation. Study records must be retained as noted above.

9 ETHICS

9.1 Institutional Review Boards

The IRB that approved this study and the approval letters will be included in the clinical study report for this protocol.

The protocol, any protocol amendments, and the ICF/IAF will be reviewed and approved by the appropriate IRB before subjects are enrolled. The Investigators or Sponsor will submit, depending on local regulations, periodic reports and inform the IRB of any reportable AEs per ICH guidelines and local IRB standards of practice.

9.2 Ethical Conduct of the Study

This study will be conducted in accordance with SOPs from both the Sponsor. These SOPs are designed to ensure adherence to GCP guidelines as required by:

- Declaration of Helsinki, 1964 (“Recommendations Guiding Physicians in Biomedical Research Involving Human Patients”), and all its accepted amendments to date concerning medical research in humans.
- ICH Guideline for GCP (Committee for Proprietary Medicinal Products/ICH/135/95) of the European Agency for the Evaluation of Medicinal Products, Committee for Proprietary Medicinal Products, ICH of Pharmaceuticals for Human Use.
- United States (US) CFR dealing with clinical studies (21 CFR, including parts 50 and 56 concerning Patient Informed Consent/Assent and IRB regulations).
- Local, national legal guidelines.

9.3 Investigators and Study Personnel

This study will be conducted by qualified Investigators under the sponsorship of Supernus Pharmaceuticals, Inc. (Sponsor).

Contact persons at the Sponsor and the qualified personnel from the site or designee are listed in the reference binder provided to each investigational site. The study will be monitored by qualified personnel from the Sponsor or their designees. Medical writing, data management, and statistical analyses will be performed by the qualified personnel

This document is confidential. It contains proprietary information of Supernus® Pharmaceuticals, Inc. Any viewing or disclosure of such information that is not authorized in writing by the Sponsor is strictly prohibited. Such information may be used solely for the purpose of reviewing or performing this study.

or designee. Laboratory tests will be conducted by a central laboratory as designated in the reference binder.

The study will be monitored by qualified personnel from Supernus or designee for data management and biostatistics groups.

9.4 Subject Information and Consent

The Investigator (or designee) will inform the caregiver and subject of all aspects pertaining to the subject's participation in the study and will provide oral and written information describing the nature and duration of the study, the procedures involved, the expected duration, the potential risks and benefits involved, and any potential discomfort.

The process for obtaining informed consent/assent will be in accordance with all applicable regulatory requirements. The Investigator (or designee) and subject/caregiver must sign and date the ICF/IAF before the subject can participate in the study. The caregiver/subject will be given a copy of the signed and dated ICF/IAF and the original will be retained in the investigational site study records.

The decision regarding subject participation in the study is entirely voluntary. The Investigator (or designee) must emphasize to the subject/caregiver that consent, regarding study participation, may be withdrawn at any time without penalty or loss of benefits to which the subject is otherwise entitled.

If the ICF/IAF is amended during the study, the Investigator must follow all applicable regulatory requirements pertaining to approval of the amended ICF/IAF by the IRB and use the amended ICF (including ongoing subjects).

10 APPENDICES

10.1 Study Definitions and ICHD-3 Diagnostic Criteria

Study Definitions

ICHD-3 outlines special features that are characteristic of migraine headaches in children and adolescents (aged under 18 years), including the following:

- In children and adolescents, migraine attacks may last 2-72 hours.
- In children and adolescents, migraine headache is often bilateral; unilateral pain usually emerges in late adolescence or early adult life.
- In children and adolescents, aura may be represented by less typical bilateral visual symptoms.
- In children, migraine headache is usually frontotemporal. Occipital headache is rare and calls for diagnostic caution.
- In young children, photophobia and phonophobia may be inferred from their behavior.

Migraine episode is defined as the occurrence of any migraine that starts, ends or recurs within a 24-hour period. Migraine episodes that persist or recur within a 24-hour period are considered the same episode.

Monthly migraine is measured by the number of migraine days within 28 days. A migraine day is defined as a calendar day (12:00 am to 11:59 pm) in which the subject experiences a migraine attack that starts, ends or recurs within 24 hours and lasts for \geq 1 hour (if untreated) or \geq 30 minutes (if interrupted with rescue medication). Pain persisting for more than 1 calendar day (\geq 24 hours) after initial onset will be considered as a new, distinct headache day.

Headache Day is any calendar day in which the subject experiences one of the following: a qualified migraine headache, a non-migraine headache that lasts continuously for more than 30 minutes, or a headache of any duration for which acute medication was used.

ICHD-3 Diagnostic Criteria

Per the IHS Criteria for Classification of Migraines in Children and Adolescents (aged less than 18 years) (<https://www.ichd-3.org/>; *Headache Classification Committee of the International Headache (IHS), Cephalalgia, 2018, 38 (1): 1-211*).

Migraine Without Aura

Previously used terms:

Common migraine; hemicrania simplex.

Description:

Recurrent headache disorder manifesting in attacks lasting 4-72 hours. Typical characteristics of the headache are unilateral location, pulsating quality, moderate or severe intensity, aggravation by routine physical activity and association with nausea and/or photophobia and phonophobia.

Diagnostic criteria:

- A. At least five attacks ^{Note #1} fulfilling criteria B-D
- B. Headache attacks lasting 4-72 h (untreated or unsuccessfully treated) ^{Notes #2; #3}
- C. Headache has at least two of the following four characteristics:
 - unilateral location
 - pulsating quality
 - moderate or severe pain intensity
 - aggravation by or causing avoidance of routine physical activity (e.g., walking or climbing stairs)
- D. During headache at least one of the following:
 - nausea and/or vomiting
 - photophobia and phonophobia
- E. Not better accounted for by another ICHD-3 diagnosis.

Notes:

1. One or a few migraine attacks may be difficult to distinguish from symptomatic migraine-like attacks. Furthermore, the nature of a single or a few attacks may be difficult to understand. Therefore, at least five attacks are required. Individuals who otherwise meet criteria for 1.1 *Migraine without aura* but have had fewer than five attacks should be coded 1.5.1 *Probable migraine without aura*.
2. When the patient falls asleep during migraine and wakes up without it, duration of the attack is reckoned until the time of awakening.
3. In children and adolescents (aged under 18 years), attacks may last 2-72 hours (the evidence for untreated durations of less than two hours in children has not been substantiated).

Migraine With Aura

Previously used terms:

Classic or classical migraine; ophthalmic, hemiparaesthetic, hemiplegic or aphasic migraine; migraine accompagnée; complicated migraine.

Description:

Recurrent attacks, lasting minutes, of unilateral fully reversible visual, sensory or other CNS symptoms that usually develop gradually and are usually followed by headache and associated migraine symptoms.

Diagnostic criteria:

- A. At least two attacks fulfilling criteria B and C
- B. One or more of the following fully reversible aura symptoms:
 - visual
 - sensory
 - speech and/or language
 - motor
 - brainstem
 - retinal
- C. At least three of the following six characteristics:
 - at least one aura symptom spreads gradually over ≥ 5 minutes
 - two or more aura symptoms occur in succession
 - each individual aura symptom lasts 5-60 minutes ^{Note #1}
 - at least one aura symptom is unilateral ^{Note #2}
 - at least one aura symptom is positive ^{Note #3}
 - the aura is accompanied, or followed within 60 minutes, by headache
- D. Not better accounted for by another ICHD-3 diagnosis.

Notes:

1. When for example three symptoms occur during an aura, the acceptable maximal duration is 3×60 minutes. Motor symptoms may last up to 72 hours.
2. Aphasia is always regarded as a unilateral symptom; dysarthria may or may not be.
3. Scintillations and pins and needles are positive symptoms of aura.

10.2 Headache Diary – Preventive Therapies (Version 2.0)

Instructions: This form should be completed by the participant for each day the participant/subject experienced a headache/migraine.

1. Did you experience a headache today? Yes No
2. What time did your headache start? (24 hour clock) Woke up with this headache
3. What time did your headache end? (24 hour clock) Headache resolved after falling asleep
4. What acute pain medication(s), in addition to the study drug, did you take? (Choose all that apply)

 Acetaminophen	 Ibuprofen
 Almotriptan	 Naproxen
 Aspirin	 Naratriptan
 Dihydroergotamine (DHE)	 Rizatriptan
 Eletriptan	 Sumatriptan
 Ergotamine tartrate (ET)	 Zolmitriptan
 Frovatriptan	 Other, specify:
5. Describe the worst severity of your headache today? Complete one of the following pain severity scales:
 - a. Which word describes the severity of your headache?
 None Mild Moderate Severe Very Severe (for cluster headaches)
 - b. Rate your overall worst pain for this headache on a scale of 0-10: ("0" = no pain & "10" = the worst pain): 0 1 2 3 4 5 6 7 8 9 10
6. Do any of the following describe your pain? (Choose all that apply)

 Throbbing	 Pressure
 Pounding	 Pulsating with the heart beat
 Stabbing	 Squeezing
 Constant	 Other, specify:
 Sharp	
7. Where is the location of your headache pain? (Choose one)
 Right Left Bilateral (both sides)
8. Where is the location of your headache pain that hurts the most? (Choose all that apply)

 Top	 All over
 One Eye (specify,  left  right)	 Right Temple
 Around Eyes	 Left Temple
 Behind Eyes	 Front
 Back	 Other, specify:
 Neck	
9. Does sound aggravate or make your headache worse? Yes No
10. Does light aggravate or make your headache worse? Yes No

11. Does routine physical activity (e.g. walking, climbing stairs) aggravate or make your headache worse? Yes No
12. Optional - Did you have any symptoms that came before and warned that this headache was going to start?
 Yes No Unknown
- a. If premonitory symptoms (symptoms that come *before* headache), which of the following did you experience? (Choose all that apply)
- | | |
|---|--|
|  Fatigue |  Yawning |
|  Difficulty concentrating |  Neck stiffness / pain |
|  Irritability |  Blurred vision |
|  Mood Changes |  Hypersensitivity to light |
|  Food Cravings |  Hypersensitivity to noise |
|  Nausea |  Other symptoms, specify: |
- b. If aura symptoms (neurological symptoms that come before or during headache), which type of aura did you have? (Choose all that apply)
- Visual aura (flashing lights, zig zag lines, dots, stars, sparkles, blind spots, shape and size distortion, temporary blindness, shimmering patches, tunnel vision, etc.)
 - Sensory aura (numbness, pins and needles)
 - Language/Speech aura (trouble understanding speech or producing it)
 - Motor aura (paralysis/muscle weakness of face, arm, or leg on one side)
 - Brainstem aura (double-vision, tinnitus or ringing in the ears, increased sense of hearing, unsteadiness when walking, slurred speech, vertigo or spinning sensation, or decreased level of alertness)
13. Did this headache reduce your ability to function? Yes No
- a. How would you describe your abilities to perform your usual daily activities at the onset of this headache?
- Able to work and function normally
 - Working ability or activity impaired to some degree
 - Working ability or activity severely impaired
 - Bed rest required
14. Did you receive acute headache treatment for your headache? Yes No
15. Complete one of the following questions:
- a. What time did this headache end? (24 hour clock)
- b. Headache ended after falling asleep? Yes No

Additional Pediatric-specific Elements

16. Did the headache change the participant's activity level (i.e., stop playing)? Yes No
17. Does activity or playing make the participant's headache worse? Yes No
18. How did today's headache affect the following school and other activities:

School

- a. Participant missed a full day of school? Yes No
b. Participant missed a half or part of the day of school? Yes No
c. Functioned at less than half of participant's ability at school? Yes No

Home

- d. Participant could not do things at home (chores, homework, etc.)? Yes No

Other Activities

- e. Participant could not participate in other activities (sports, play, etc.)? Yes No
f. Participant functioned at less than half of his/her ability? Yes No

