6 STUDY VARIABLES AND ASSESSMENTS

6.1 Headache Diary– Preventive Therapies (Version 2.0)

The Headache Diary ([Appendix 10.2](#)) is the primary tool for collecting information about migraine headaches and will be used in the format recommended by the NINDS. The diary will serve as the primary source for the primary outcome measure of MMDs. The diary will be provided to caregivers in an electronic format as an application and uploaded on the caregivers' personal mobile device or on a dedicated locked mobile device in case the caregiver does not have a personal device. Reminder alarms will be programmed for diary completion and SM administration to ensure regular data entry and treatment compliance.

The caregiver will enter data with the subject's assistance every day during the Prospective Baseline Period and throughout the duration of treatment, regardless of whether they experienced a headache.

Subject's caregivers will be trained to complete a prospective 28-day headache calendar to document if a headache occurred. Based on the diagnostic criteria for migraine (ICHD-3), if the subject experienced a migraine headache as documented in the calendar, the diary will be completed to record headache specific and detailed information.

For any given headache day, the responder will include information about the timing of the attack (when the headache started and ended and whether or not it recurred within a 24-hour period), the location and severity of the pain, premonitory and aura symptoms (nausea, photophobia and phonophobia), rescue medications (if used, selected from a list), the impact of the headache on subject's daily activities, and treatment adherence after randomization. Severity of pain will be measured on a scale of 0 to 10, where 0 = No pain and 10 = The worst pain.

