## 4. Definitions and Derivations

- 1) Baseline: Unless specified otherwise, baseline is defined as the non-missing value collected most recent to and before the time of the very first dose of the SM.
- 2) The 28-day rate for the prospective baseline = (total number of migraine days during the last 4 weeks prior to randomization/ total number of days prior to randomization) \*28.
- 3) Headache Day is any calendar day in which the subject experiences one of the following: a qualified migraine headache, a non-migraine headache that lasts continuously for more than 30 minutes, or a headache of any duration for which acute medication was used.
- 4) Severity of Headache is rated on a scale of 0-10: 0=None, 1- 3=Mild, 4-6=Moderate, 7-9=Severe, 10=Very severe.
- 5) Migraine is defined as any headache with or without aura that meets **both A and B**

**criteria** as described below (with matched question #s in 538P401 Protocol Appendix 2 Headache Diary).

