**B Criteria:**

At least **two** of the following:

- 1) Unilateral location:

*Question #7 checked with either Right or Left.*

- 2) Pulsatile quality:

*Question #6 checked with at least one of (throbbing, pounding, stabbing, constant, sharp, pressure, pulsating with the heartbeat, squeezing or other).*

- 3) At least moderate pain intensity:

*Question #5b rated  $\geq 4$  in the pain scale*

- 4) Aggravation by physical activity:

*Question #11 checked yes*

- 6) Headache/Migraine Duration is defined as the difference between the headache end date time minus start date time.
- 7) Change from Baseline = value at current time point – value at baseline.
- 8) Treatment Emergent Adverse Event (TEAE) = any adverse event with an onset date/time after first dose of study medication.
- 9) Duration of Adverse Event = AE end date – AE start date + 1
- 10) Duration of Treatment Exposure = date of last dose – date of first dose + 1
- 11) Percent of Study Medication Compliance is calculated as

$\% \text{ compliance} = 100 * (\text{Num}/\text{Den})$ , where

$$\text{Num} = \sum_{i=3}^7 \# \text{ of capsules dispensed at } \text{visit}_i - \# \text{ of capsules returned at } \text{visit}_{i+1}$$

$$\text{Den} = \sum_{i=3}^7 x_i \times (\# \text{ of days between } \text{visit}_i \text{ and } \text{visit}_{i+1}), \text{ where}$$

$x_i = \# \text{ of capsules per day assigned to be administered at } \text{visit}_i$

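### A headache rated only by word in diary item 5a cannot meet the SAP's pain-intensity criterion, which reads only the 0–10 score in item 5b

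*Protocol*

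**What the plan says.** The diary form in Protocol Appendix 10.2 introduces Question 5 with "Describe the worst severity of your headache today? Complete one of the following pain severity scales". Item 5a asks "Which word describes the severity of your headache" and offers None, Mild, Moderate, Severe and Very Severe, the last marked as being for cluster headaches. Item 5b asks the respondent to "Rate your overall worst pain for this headache on a scale of 0-10".

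The body of the protocol names one scale only. Section 6.1 states that "Severity of pain will be measured on a scale of 0 to 10". The same section points to Appendix 10.2 for the form.

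SAP Section 4 ties its migraine definition to diary question numbers. Criterion B3, "At least moderate pain intensity", is assessed from "Question #5b rated" 4 or higher. Item 4 of that section begins "Severity of Headache is rated on a scale of 0-10" and cuts the number into the mild, moderate, severe and very severe categories that the severity endpoint in SAP Section 5.2 uses. The available text has no rule that uses 5a and none for a blank 5b.

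**The concern.** A caregiver who ticks Severe in 5a and leaves 5b empty has followed the form, but the analysis rule does not read that answer. A blank 5b is not a score of 4 or more, and SAS, the stated software, evaluates that comparison as false without warning.

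A migraine needs at least two B criteria, so losing B3 can turn a migraine into a non-migraine headache. The day then adds nothing to the migraine-day count. Because its headache record is not missing, it stays in the denominator of the 28-day rate (SAP Section 5.1). The primary, responder and onset endpoints share that count. Baseline counts, and with them the strata and the eligibility check, are also touched if they are derived by the same rule. In the severity summary the day sits in the denominator but in no category.

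**Working it through.** **Plan's own figure.** Protocol Section 7.9 gives a difference of 1.1, SD 3, two-sided 0.05 and 80% power. n per arm = 2 × (1.96 + 0.8416)² × 3² / 1.1² = 116.8, rounded up to 117. Exact t-test power at 117 per arm is 79.8%. With 15% dropout, 234 / 0.85 = 275.3, giving 276. The sample size reproduces and is not in dispute.

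**Which headaches change status.** Take a headache that meets the A criteria and is truly at least moderate. The rule is at least two of B1 (one-sided pain), B2 (pain quality), B3 (intensity) and B4 (aggravated by activity). Enumerate B1, B2 and B4:

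| Case | Patterns | Migraine if 5b is filled (B3 met) | Migraine if only 5a is filled (B3 not met) |
|---|---|---|---|
| B1, B2, B4 free | 8 | 7 | 4 |
| B2 always met | 4 | 4 | 3 |

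The three patterns lost in the first row are those with exactly one of B1, B2 and B4.

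The second row is closer to practice, because B2 needs Question 6 only to be "checked with at least one of (throbbing, pounding, stabbing, constant, sharp, pressure, pulsating with the heartbeat, squeezing or other"). The single pattern lost there is bilateral pain not aggravated by activity. Bilateral pain is not unusual here: Protocol Appendix 10.1 describes it as frequent in paediatric migraine.

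**Share of migraine days lost.** Loss = q × r, where q is the share of migraine headaches rated in 5a only and r is the share that needs B3 to reach two criteria. The documents give neither, so both are assumptions.
- q = 10%, r = 20%: 0.10 × 0.20 = 2%.
- q = 20%, r = 40%: 0.20 × 0.40 = 8%.
- q = 30%, r = 60%: 0.30 × 0.60 = 18%.

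A wider illustration takes B2 as always met and B1 and B4 as independent, so that r = P(bilateral) × P(not aggravated). With q 10–50%, bilateral 50–90% and not aggravated 20–60%, the loss runs from 0.10 × 0.50 × 0.20 = 1% to 0.50 × 0.90 × 0.60 = 27%.

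**Effect on the treatment difference.** If the same fraction f is lost in both arms and in both periods, the difference becomes 1.1 × (1 − f).
- f = 2%: reduction 0.02 × 1.1 = 0.022 day.
- f = 18%: reduction 0.18 × 1.1 = 0.198 day.
- f = 27%: reduction 0.27 × 1.1 = 0.297 day.

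**Effect on power at 117 per arm.**

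| f | Difference | Power, SD held at 3 | Power, SD shrinks with the count |
|---|---|---|---|
| 0% | 1.100 | 79.8% | 79.8% |
| 5% | 1.045 | 75.6% | 79.8% |
| 10% | 0.990 | 71.0% | 79.8% |
| 20% | 0.880 | 60.8% | 79.8% |

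**The case against.** The best reply is that the intended scale is clear. Section 6.1 and both SAP definitions use 0–10, and only the appended form, a generic NINDS instrument, offers a choice. Its cluster-headache label on Very Severe shows wording not tailored to this trial, since cluster headache is excluded. Data come through an electronic application whose screens are not shown. If it requires 5b, nothing is lost. SAP Section 6.7.1, on missing efficacy data, is not in the available text and may deal with a blank 5b.

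This stands as a limit on size. It does not remove the conflict: Section 6.1 adopts the form that carries the instruction to complete one scale, and nothing visible says that the application overrides it.

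A reader might also infer that the loss could match the whole planned effect, since 18% of an assumed 6 migraine days is 1.08 days, close to 1.1. The documents do not support that. The 1.08 days is an undercount in the level of migraine days, while 1.1 is a difference between arms. Both arms use the same diary under blinding, so a common proportional loss shrinks the difference and does not cancel it.

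Nor do the documents support a bias in the Month 5 contrast from caregivers switching between 5a and 5b over time. Switching could distort change within an arm, but nothing in the documents suggests that it would differ by arm.

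The severity endpoint is summarised descriptively only (Protocol Section 7.8.3), so the harm there is small.

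**Conclusion.** The concern holds as an unreconciled conflict in the algorithm for the primary endpoint: a diary record completed as instructed can be scored as a non-migraine headache. The logic follows directly from the form and the B criteria and needs no assumption.

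The size does rest on assumptions. It is zero if the application forces 5b. Otherwise the likely result is attenuation of about 0.02–0.2 day out of 1.1, for an assumed loss of 2–18% that is equal across arms and periods. Whether power falls depends on whether the SD shrinks along with the counts. The planned sample size is unaffected. The matter should be settled now because any handling of a blank 5b chosen after unblinding would be post hoc.

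**What to change.** First establish whether the electronic diary accepts 5a without 5b.

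- **If 5b can be blank:** amend SAP Section 4 before unblinding. Let B3 be met by 5b ≥ 4 or, when 5b is blank, by 5a = Moderate, Severe or Very Severe. Take the severity category from 5a when 5b is blank. Apply the same derivation to the baseline and treatment periods. Add a sensitivity analysis of the primary endpoint using 5b only.
- **If 5b is already compulsory:** say so in the SAP and correct Appendix 10.2 to match Section 6.1.

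Do not change the instrument for children already enrolled. Protocol Version 4.0 provides for rescreening subjects who failed screening under earlier versions, so screening was under way. A mid-study change could leave baseline and Month 5 measured differently.

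The cost is a few lines of SAP text, one programming rule and one extra model run, with no added patient burden. The small downside is that equating the words with score bands is an assumption that the documents do not validate. The 5b-only analysis shows how much depends on it.
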